The prior mean for the probability of DLT for the six doses (i.e. the power model skeleton) are 3%, 5%, 7%, 10%, 14% and 20%, respectively. As the study progresses, updated probabilities of DLT are computed before each new cohort of patients is enrolled and both patients of each cohort have reached Day 28 (end of the DLT assessment period) prior to enrollment of a subsequent cohort. Each subsequent cohort will be assigned to the most appropriate dose based on these updated probabilities. Eventually the final dose (within our proposed sample of 30 patients) will be identified as the dose most closely associated with a DLT rate of 20%. To promote patient safety: 1) we will enroll cohorts of 2 patients starting at the 1st dose; and 2) dose levels will not be skipped when escalating.

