#### **Phase I Dose Finding Component:**

The Phase I component uses a continual reassessment method (CRM) to determine the maximum tolerated dose (MTD) of GTB-3550 TriKE. Up to 7 doses levels will be tested. The goal of the CRM is to identify the dose level which most closely corresponds to the targeted dose limiting toxicity (DLT) rate of 20%. Patients are enrolled in cohorts of 2 beginning at Dose Level 1. A minimum of 1 week must separate each patient. Both patients within a cohort must reach Day 28 (end of the DLT assessment period) prior to enrollment of a subsequent cohort. The study statistician assigns each new cohort of 2 patients to the most appropriate dose level based on updated toxicity probabilities. As enrollment proceeds, each cohort is assigned to an increased, decreased or equivalent dose level based on prior data in the trial until the study sample reaches 30. At this time, the last dose is declared the MTD and becomes the GTB-3550 TriKE dose for the extended component.

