**Extended Phase II Component:**

Patients will receive three consecutive blocks of four 24 hour continuous infusions of GTB-3550 TriKE at the Phase I MTD separated by a 72 hour rest. There is no staggering of enrollment for this component.

**Stage 1:** Enroll a total of 13 patients (including all treated at the MTD in Phase I). If 3 or more of these patients have clinical response by Day 42 the trial will continue to Stage 2. If the Phase I component enrolls more than 13 patients at the MTD, the futility rule for the two-stage design will be adjusted with the given number of patients enrolled at the MTD.

**Stage 2:** Enroll an additional 17 patients. If 10 of 30 patients have a clinical response by Day 42, GTB-3550 TriKE will be considered promising for further investigation.

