## 4 Study Design

This is a multisite Phase I/II clinical trial of GTB-3550 (CD16/IL-15/CD33) tri-specific killer cell engager (TriKE) for the treatment of CD33-expressing high risk myelodysplastic syndromes, refractory/relapsed acute myeloid leukemia or advanced systemic mastocytosis. Up to 10 study centers may take part in this trial.

Patients receive a single course of GTB-3550 TriKE given as 3 weekly treatment blocks. Each block consists of four consecutive 24 hour continuous infusions of GTB-3550 TriKE followed by a 72 hour break after Block #1 and #2. All treatment is given as an inpatient.

Toxicities are monitored through Day 28 (as assessed on Day 29) with continued toxicity assessment through Day 60. Disease response is assessed by bone marrow biopsy performed between Day 21 and 42 after the start of the 1st infusion. Follow-up for response and survival continues through 6 months from study treatment start.

The study consists of two components. The dose finding component is a modified version of a Phase I trial and the extended component is a modified Phase II trial.

**Dose Finding Component:** The Phase I component uses a continual reassessment method (CRM) to determine the maximum tolerated dose (MTD) of GTB-3550 TriKE. Up to 7 doses levels will be tested. The goal of the CRM is to identify the dose level which most closely corresponds to the targeted dose limiting toxicity (DLT) rate of 20%.

Patients are enrolled in cohorts of 2 beginning at Dose Level 1. A minimum of 1 week must separate each patient. Both patients within a cohort must reach Day 28 (end of the DLT assessment period) prior to enrollment of a subsequent cohort. The study statistician assigns each new cohort of 2 patients to the most appropriate dose level based on updated toxicity probabilities. As enrollment proceeds, each cohort is assigned to an increased, decreased or equivalent dose level based on prior data in the trial until the study sample reaches 30. At this time, the last dose is declared the MTD and the GTB-3550 TriKE dose for the extended component.

**Extended Component:** The primary goal of the extended component is to study the potential efficacy of GTB-3550 TriKE in this patient population. Efficacy is measured using rates of complete and partial remission. A Simon's MiniMax two-stage design is used in this phase. Monitoring guidelines are in place to stop the study early for excessive toxicity.

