## **Phase II Extension: Studying the efficacy of GTB-3550 TriKE for the endpoint of objective response:**

After completion of the dose finding trial, the final dose will be carried forward into an uncontrolled two-stage Phase II extension trial to confirm safety and make a preliminary determination of the activity level. For advanced MDS/AML, the lack of

defined effective alternative therapies precludes a control regimen for comparisons at this stage of testing. If the Phase I trial enrolls fewer than 14 patients at the MTD, we will employ a Simon's Minimax two-stage design with the possibility to discontinue after the 1st stage if the response rate is low.

- Stage 1: Enroll a total of 13 patients (including all treated at the MTD in Phase I). If 3 or more of these respond, the trial will continue to stage 2.
- Stage 2: Enroll an additional 17 patients. If 10 of 30 patients respond, GTB-3550 TriKE will be considered promising for further investigation.

If the Phase I trial enrolls more than 13 patients at the MTD, we will adjust the futility rule above for the two-stage design with the given number of patients enrolled at the MTD.

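### The protocol gives two different rules for declaring the MTD; they often name different dose levels, and one of them does not require that the declared level was ever given

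*Combined protocol and SAP*

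**What the plan says.** - **Synopsis, Phase I Dose Finding Component**, once the sample reaches 30: "At this time, the last dose is declared the MTD and becomes the GTB-3550 TriKE dose for the extended component". **Section 4** has the same rule: "the last dose is declared the MTD and the GTB-3550 TriKE dose for the extended component".
- **Section 12.1, Phase I component**: the dose that results from Phase I "will be identified as the dose most closely associated with a DLT rate of 20" percent. A parenthesis earlier in that sentence ties this dose to the planned 30 patients. The Study Schema, Section 7.2.1 and the start of the Phase I text in Section 12.1 also define the MTD by closeness to a 20% DLT rate.
- **Section 12.1, safeguards**: there are two. Cohorts of 2 start at the first dose, and "dose levels will not be skipped when escalating". Both concern the assignment of cohorts.
- **Section 12.1, Phase II Extension**: "the final dose will be carried forward into an uncontrolled two-stage Phase II extension trial". The Study Schema says of Phase II: "There is no staggering of enrollment for this component".
- **Sections 12.3 and 12.4**: the total may reach 57, and the Phase II toxicity boundary assumes 27 patients enrolled after Phase I.

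**The concern.** The MTD declaration is the Phase I result, and it fixes the Phase II dose. It also decides which Phase I patients count toward the 13 in Stage 1. A CRM assigns each cohort from the data before it, so the last dose given does not use the last cohort's own outcomes. A closest-to-20% rule applied at 30 patients does use them. Unless the last two outcomes leave the recommendation where it was, the two rules give different doses from the same data.

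The Section 12.1 rule also carries no condition that the chosen level was given. The last update can therefore move one level above the highest level tried. Phase II would then be the first use of that level, without the one-week separation of patients and the Day 28 gate of Phase I.

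**Working it through.** **1. The plan's own sample-size figure.** 30 in Phase I + 27 additional = 57, as Section 12.3 states. Since Phase II needs 30 at the MTD, 27 additional implies 30 - 27 = 3 Phase I patients already at the MTD. The documents do not state this 3, and no rule enforces it. With an untried MTD the maximum would be 30 + 30 = 60.

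**2. Inputs for the CRM check.**
- Section 12.1: P(DLT at level i) = d_i^exp(α), with α ~ N(0, variance 0.5) and target 20%.
- Section 12.1: printed skeleton of 3, 5, 7, 10, 14 and 20%. The revision note adds 17% for the new level. I read this as the seventh skeleton value, giving 3, 5, 7, 10, 14, 17, 20%.
- Section 7.2.1 and the Synopsis: 30 evaluable patients in cohorts of 2, that is 15 cohorts, from Level 1. Section 12.1 adds that untried levels are not skipped.
- Section 12.4: stop if the posterior probability that Level 1 exceeds the target is above 90%.
- Assumed: the true DLT curves, because Table 1 is not shown. The 50% increments after immune activation (Section 7.2.1) are not modelled.

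**3. One trial in which the rules part.** Level and DLTs out of 2, cohort by cohort: 1:0, 2:0, 3:0, 4:0, 5:1, 6:1, 5:1, 4:0, 5:0, 5:0, 6:0, 6:1, 5:0, 6:0, 6:0.
- Totals for Levels 1 to 7: 2, 2, 2, 4, 10, 10 and 0 patients; 0, 0, 0, 0, 2, 2 and 0 DLTs.
- Before the last cohort (8 patients at Level 6), the posterior means are 19.1% at Level 6 and 22.1% at Level 7. Distances from 20% are 0.9 and 2.1, so Level 6 is assigned.
- After the last cohort, they are 17.9% at Level 6 and 20.8% at Level 7. Distances are 2.1 and 0.8, so the closest level is Level 7.
- Synopsis and Section 4 rule: Level 6, with 10 patients. Section 12.1 rule: Level 7, with none. Plugging the posterior mean of α into the model gives the same choice.

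**4. Frequencies.** Seven-value skeleton, 20,000 trials per curve, posterior mean / plug-in estimate:

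| Assumed true curve | Rules differ, % | MTD untried, % |
|---|---|---|
| Equal to skeleton | 22.5 / 22.1 | 2.2 / 1.9 |
| 1.5 × skeleton | 34.9 / 34.8 | 2.3 / 1.9 |
| 2 × skeleton | 37.8 / 37.7 | 1.9 / 1.4 |
| MTD at Level 5 | 35.9 / 36.7 | 1.9 / 1.6 |
| MTD at Level 3 | 39.1 / 39.1 | 1.2 / 0.6 |
| MTD at Level 1 | 18.0 / 18.7 | 0.4 / 0.2 |
| Half of skeleton | 4.5 / 4.1 | 0.8 / 0.6 |

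Over all eleven curves run, the rules differ in 4-39% of trials and the MTD is untried in 0.2-2.3%. Smaller separate runs on narrower sets of curves gave about 18-40% and up to 2.5%. With the six printed skeleton values only, the untried share is 0.2-1.8%. Every untried MTD was exactly one level above the highest level given.

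**5. True toxicity at the untried level.** The mean true DLT rate there was about 24-35% when the true MTD was at Levels 3-6. It was about 17-18%, below the target, when the true rates equalled the skeleton or the true MTD was Level 7. The skeleton curve is among those where the event is most frequent.

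**6. Effect of restricting the estimate to tested levels.** The untried share becomes 0 by construction. Correct selection hardly moved with the true MTD below the top level (for example 39.1 against 39.3%, and 43.9 against 44.0%). With the top level correct it fell, for example from 57.7 to 56.4%.

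**The case against.** A reader might infer that the protocol as it stands lets Phase II open at a dose nobody has received, because the no-skipping limit does not reach the final estimate. The documents do not support that, for three reasons.

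- The Synopsis and Section 4 rule, read plainly, names a dose already given. Only Section 12.1 read alone allows an untried level. Even there, the parenthesis about the sample of 30 can be read as a dose given within that sample. The allowance of 27 additional patients points the same way, although as an assumption and not a rule.
- No-skipping is not the cause. Each overshoot is the next level up, which that limit permits, so extending it to the final estimate would change nothing. What is missing is a statement on whether the declared level must have been tested.
- The event is uncommon, and the untried level is not always above target. Phase II keeps inpatient treatment, ends a patient's treatment at a DLT, and has continuous toxicity and mortality boundaries that start at 2 events in 3 patients.

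It can also be said that the last dose is loose wording for the model's last recommendation, so that only one rule was meant. That is possible, but the text does not say it, and under that meaning the untried level returns. Either reading leaves something to settle.

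**Conclusion.** The protocol contains two MTD-declaration rules that are not equivalent. Under the stated CRM they give different Phase II doses in roughly 18-40% of trials, or 4-39% over the wider set of curves. An untried MTD arises only under the Section 12.1 rule, in about 0.2-2.5% of trials, and the maximum total would then be 60, not 57. It is a secondary reason to settle the rule, not a demonstrated flaw of the whole protocol.

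The frequencies rest on assumed true curves, on 17% as the seventh skeleton value, and on ignoring the immune-activation increments. The existence of the conflict rests on the text alone.

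**What to change.** Reconcile the Synopsis and Section 4 with Section 12.1 into one rule and use the same words in all three places. The rule should say:

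1. whether the model is updated after the last cohort before the MTD is declared;
2. whether the final estimate is restricted to levels at which a cohort has completed the DLT assessment.

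Then rerun the Table 1 operating characteristics under that rule, and check that the 27 additional patients and the maximum of 57 agree with it. Which level should go forward in a given case is for the sponsor and investigators to settle.

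The cost is a few sentences and one rerun. If the restriction is adopted, the declared level is one lower in up to about 2.5% of trials, and correct selection falls by about 1 percentage point when the top level is the true MTD (57.7 - 56.4 = 1.3 in the run above).

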## **Phase II Extension: Studying the efficacy of GTB-3550 TriKE for the endpoint of objective response:**

After completion of the dose finding trial, the final dose will be carried forward into an uncontrolled two-stage Phase II extension trial to confirm safety and make a preliminary determination of the activity level. For advanced MDS/AML, the lack of

defined effective alternative therapies precludes a control regimen for comparisons at this stage of testing. If the Phase I trial enrolls fewer than 14 patients at the MTD, we will employ a Simon's Minimax two-stage design with the possibility to discontinue after the 1st stage if the response rate is low.

- Stage 1: Enroll a total of 13 patients (including all treated at the MTD in Phase I). If 3 or more of these respond, the trial will continue to stage 2.
- Stage 2: Enroll an additional 17 patients. If 10 of 30 patients respond, GTB-3550 TriKE will be considered promising for further investigation.

If the Phase I trial enrolls more than 13 patients at the MTD, we will adjust the futility rule above for the two-stage design with the given number of patients enrolled at the MTD.

## 12.2 Statistical Analysis

Response will be estimated with simple proportions and descriptive plots. The secondary endpoint of OS will be estimated with Kaplan-Meier curves. Safety measures will be described with frequencies and proportions.

The change in number, phenotype and function of NK cells from baseline to the end of treatment will be correlated with clinical response using appropriate regression analyses such as Cox or Logistic regression. Assessment of serum TriKE levels will be determined using descriptive statistics.

### 12.3 Sample Size Justification

## Trial Size Determination:

Assuming a target DLT probability of 20%, an effect size or odds ratio of 1.7 and a commonly used accuracy index of 0.5, the initial sample size is 27. We conservatively rounded to 30 patients.

Operating characteristics for various 'true' probabilities are listed in [Table 1](#).

Table 1.

If fewer than 14 patients are enrolled at the MTD, the Phase II extension trial using the Simon's two-stage design will require 30 patients to test the null hypothesis that the response rate is <20% versus the alternative that the response rate is  $\geq 40\%$  after assuming 80% power and a significance level of 0.05.

If the Phase I trial enrolls more than 13 patients at the MTD, we will adjust the futility rule of the two-stage design while maintaining the constraints of 80% power, a significance level of 0.05 and using a maximum of 30 patients. We will choose the rule that minimizes the expected sample size given a true response rate equivalent to the null hypothesis. We expect that approximately 44 patients will be required due to use of patients from the Phase I trial in the Phase II extension but the sample size may be as high as 57. Enrollment is expected to be 1-2 patients per month.

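### The Phase II rule (3 of 13, then 10 of 30) has an exact type I error of 5.8%, not 5%, and the fallback for more than 13 patients at the MTD sets constraints that no rule on 30 patients can meet

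*Combined protocol and SAP*

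**What the plan says.** Section 12.1 (Phase II Extension) states that, with fewer than 14 patients at the MTD, "we will employ a Simon's Minimax two-stage design". Stage 1 has 13 patients, including those treated at the MTD in Phase I: "If 3 or more of these respond, the trial will continue to stage 2". Stage 2 adds 17: "If 10 of 30 patients respond, GTB-3550 TriKE will be considered promising for further investigation". The Synopsis and Section 4 word the final threshold as at least 10 of 30.

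Section 12.3 gives the design basis. The 30 patients are to "test the null hypothesis that the response rate is <20% versus the alternative" of 40% or more, "after assuming 80% power and a significance level of 0.05". If Phase I places more than 13 patients at the MTD, the futility rule will be adjusted "while maintaining the constraints of 80% power, a significance level of 0.05 and using a maximum of 30 patients". Among the rules that qualify, the one with the smallest expected sample size under the null is to be chosen.

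**The concern.** The continuation rule, the success threshold and both hypotheses are given, so the error rates can be computed exactly. They should agree with the stated 5% and 80%. If the type I error is above 5%, the go/no-go threshold does not have its advertised property.

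The fallback raises a second question. It asks for the best rule within three limits, which presupposes that at least one rule satisfies all three. If none does, the statistician must give up one of them at the end of Phase I. The fallback patients are Phase I patients treated at the MTD, so many of their responses may be known by then. The choice of which limit to break could then be influenced by the data.

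**Working it through.** **Inputs.** From Section 12.3: p0 = 0.20, p1 = 0.40, significance level 0.05, power 0.80. From Section 12.1: n1 = 13, continue if at least 3 respond, 17 more patients, N = 30, success if at least 10 respond. Sidedness is not stated. The hypotheses are directional, so one-sided is used.

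**1. The stated rule.** The probability of declaring success at response rate p is

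P(p) = Σ (x = 3 to 13) Bin(x; 13, p) × P[Bin(17, p) ≥ 10 − x].

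Terms at p = 0.20:

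| x of 13 | Bin(x; 13, 0.2) | P[Bin(17, 0.2) ≥ 10 − x] | product |
|---|---|---|---|
| 3 | 0.24567 | 0.03766 | 0.00925 |
| 4 | 0.15355 | 0.10570 | 0.01623 |
| 5 | 0.06910 | 0.24178 | 0.01671 |
| 6 | 0.02303 | 0.45112 | 0.01039 |
| 7 | 0.00576 | 0.69038 | 0.00398 |
| 8 | 0.00108 | 0.88178 | 0.00095 |
| 9 or more | | | 0.00016 |

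The sum is **0.0577**. The same formula at p = 0.40 gives **0.8051**. The stated power reproduces and the stated 0.05 does not. The excess is 0.0577 − 0.05 = 0.0077.

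**2. Nearby readings.** None gives both 5% and 80%.

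| Rule | Type I error | Power |
|---|---|---|
| ≥3/13, then ≥10/30 (as written) | 0.0577 | 0.805 |
| ≥4/13, then ≥10/30 | 0.0484 | 0.744 |
| ≥3/13, then ≥11/30 | 0.0248 | 0.698 |
| ≥10/30, futility stop ignored | 0.0611 | 0.824 |
| ≥11/30, futility stop ignored | 0.0256 | 0.709 |

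**3. Is any rule on at most 30 patients feasible?** Enumerating all two-stage rules with N ≤ 30 finds none with type I error ≤ 0.05 and power ≥ 0.80.
- The best power with type I error ≤ 0.05 is 0.785 (success at ≥10/29, type I error 0.0493).
- The smallest type I error with power ≥ 0.80 is 0.0568 (≥6/21, then ≥10/30).
- Both extremes are unchanged when n1 is restricted to 14 or more, which is the fallback case.

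A general bound confirms this. The most powerful level-0.05 test on 30 patients rejects at ≥11 and, when exactly 10 respond, rejects with probability

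g = (0.05 − 0.02562) / (0.06109 − 0.02562) = 0.687.

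Its power is 0.7085 + 0.687 × (0.8237 − 0.7085) = **0.788**. No rule on at most 30 patients can exceed this, whatever its stages.

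**4. The fallback at N = 30.** For n1 = 14 to 28, the best power with type I error ≤ 0.05 is 0.71 to 0.77. Keeping power ≥ 0.80 needs a type I error of 0.057 to 0.060. With n1 = 29 or 30 the design is in effect single-stage, at 0.0611.

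**5. Smallest feasible maximum.** No rule with N = 31 or 32 qualifies. At N = 33 the minimax rule is ≥5/18, then ≥11/33, with type I error 0.0458, power 0.8011 and expected N under the null 22.3.

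**The case against.** The strongest case on the other side concerns weight, not arithmetic. The extension is uncontrolled and preliminary. Success means only that the agent merits further study, and Section 12.2 analyses response descriptively. An excess of 0.8 percentage points with power met changes no decision if the thresholds stay as they are. That stands: in the main branch this is a misreported operating characteristic.

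On the fallback, Section 12.3 does fix an objective selection criterion, the smallest expected sample size under the null. Once the type I error limit is relaxed slightly, that criterion picks one rule for each n1. The documents also do not say when the rule would be recomputed, so it is an inference that responses would already be known. Both points are fair, but neither rescues the instruction. The criterion selects only within a feasible set, that set is empty, and the plan does not say which limit gives way.

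The unstated sidedness does not help. Reading 0.05 as two-sided (0.025 per side) raises the minimax N to 41.

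**Conclusion.** The concern holds in both parts. The stated rule has a one-sided exact type I error of 0.0577 and power 0.805. The fallback asks for 5%, 80% and at most 30 patients together, which is impossible; 33 is the smallest maximum that meets both error limits. The fallback is the reason this needs correcting before it is used.

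The figures treat the futility stop as binding, count all 30 patients as evaluable, and ignore any effect of carrying Phase I patients into the extension. The rule is exactly the minimax design for a limit of 0.06, so it may have been generated at that level and reported as 0.05; that origin is a guess.

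**What to change.** In Section 12.3, state the operating characteristics of the 3/13, 10/30 rule as one-sided exact type I error 0.058 and power 0.805.

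For the branch with more than 13 patients at the MTD, replace the 0.05 limit with an attainable one. At N = 30 with power at least 80%, a limit of 0.062 can be met for every n1 from 14 to 30; a limit of 0.061 would just miss at 29 and 30. Keep the expected-sample-size criterion and tabulate the resulting rule for each n1 now. Examples, all with success at 10 or more of 30:

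| n1 | Continue if | Type I error | Power |
|---|---|---|---|
| 16 | ≥4 | 0.0577 | 0.807 |
| 20 | ≥5 | 0.0595 | 0.817 |
| 24 | ≥7 | 0.0581 | 0.813 |

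This costs wording, one small table and a slightly less favourable stated error rate. It adds no patients.

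If 5% must hold, the sponsor has two choices:
- Keep N = 30, require 11 of 30, and state power of about 70%.
- Keep 80% power by raising the maximum to 33, for example ≥5/18 then ≥11/33. That is 3 more patients, so the stated upper total of 57 becomes 60. The stopping boundaries in Section 12.4, which assume 27 additional patients, would need recalculating.

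Under either choice, the thresholds in the Synopsis, the Study Schema and Sections 4, 7.2.2 and 12.1 must be changed to match.
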